Appendix 5 KS Lesion Assessment/ Photography Protocol

INTERNATIONAL COLLABORATIVE	Participant ID Number	Interviewer Initials	Date of Visit	Visit Number
	□□□□□□□	□□□	□□/□□□/□□□ □ Day Month Year	□□
	Reviewer Initials	Date of Review	Interim Visit Number	
	□□□	□□/□□□/□□□ □ Day Month Year	□□	

KS LESION ASSESSMENT

A "KS-suspicious" lesion is defined as a lesion that is either known to be KS (by virtue of biopsy) or clinically suspected to be KS. In the questions below, when asked about KS-suspicious lesions, consider only those which are **hyperpigmented** with the usual characteristics of KS, regardless if they are flat or raised. Do not count lesions which have subcutaneous swelling alone, without hyperpigmentation, as KS-suspicious.

A. Overall Cutaneous Do not count oral cavity lesions.

1. Overall inventory: How many KS-suspicious lesions are present? 1-49 ≥ 50

2. Indicate if KS-suspicious lesions are absent or present in each of these sites.

Site #	Absent	Present	Site #	Absent	Present	Site #	Absent	Present
12 – Head			17 – Right arm			22 – Left hand		
13 – Neck			18 – Left arm			23 – Right foot		
14 – Chest			19 – Right leg			24 – Left foot		
15 – Abdomen			20 – Left leg			25 – Genital		
16 – Back			21 – Right hand			26 – Gluteal		

Lesion Counts

Include only KS-suspicious lesions (do not include lesions with subcutaneous swelling alone).

If ≥ 50 lesions overall, select three sites that are **most representative** of the total body in terms of lesion characteristics and which have a combined lesion count of at least 50. If three such areas cannot be found which total at least 50 lesions, choose 3 areas with the largest combined count. Indicate the sites using the corresponding codes above. Do not use the mouth. If lesions are only present in the mouth, go to question 4.

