1.0 Synopsis of Study Design Procedures

This study will enroll up to fourteen (14) HIV (human immunodeficiency virus) - positive female or male subjects at least 18 years of age who have biopsy-confirmed Kaposi Sarcoma (KS).

The primary objective of this study is:

- To determine the safety of escalating doses of Tc 99m tilmanocept in HIV subjects with biopsy-confirmed KS

The secondary objectives of this study are:

- Concordance between clinical assessment/diagnosis and the localization of Tc 99m tilmanocept by planar and/or SPECT (single photon emission computed tomography) / CT (X-ray computed tomography) imaging in cutaneous and non-cutaneous sites of KS.
- Qualify and quantify Tc 99m tilmanocept localization intensity on imaging with CD206 locale and quantity by histology and immunohistochemistry (IHC) in biopsied KS lesions to determine optimal IV dose.
- Concordance of localization of Tc 99m tilmanocept via IV and SC routes of administration by planar and/or SPECT/CT imaging in cutaneous and non-cutaneous sites of KS.

The exploratory objective of this study is:

- Quantify HHV8 in biopsied KS lesions by real-time polymerase chain reaction (qPCR)

General safety will be evaluated by examining the incidence of adverse events (AEs) and changes over time in laboratory tests, vital signs, ECGs (electrocardiogram) and physical examination findings.

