1.1.1 Localization Definitions

A localized subject is one for whom Tc 99m tilmanocept by planar and/or SPECT/CT imaging results in the illumination of at least one site relative to background as determined by the nuclear medicine specialist.

A localized KS lesion is a lesion that is both clinically identified or suspected KS (via biopsy-confirmed diagnosis or clinical symptomatology) and is illuminated by planar and/or SPECT/CT imaging.

Localization in areas other than KS will also be defined per subject and per area, where these areas are clinically negative KS locations based on clinical symptomatology.

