4.0 Analysis of Efficacy

4.1 Description of Efficacy Variables

Secondary objectives of the study are to determine the concordance between clinical assessment/diagnosis and the localization of Tc 99m tilmanocept by planar and/or SPECT/CT imaging in cutaneous and non-cutaneous sites of KS; to qualify and quantify Tc 99m tilmanocept localization intensity on imaging with CD 206 locale and quantity by histology and IHC in biopsied KS lesions to determine the optimal IV dose; and concordance of localization of Tc 99m tilmanocept via IV and SC routes of administration by planar and/or SPECT/CT imaging in cutaneous and non-cutaneous sites of KS. The relevant endpoints are the following:

- Per subject localization rate of Tc 99m tilmanocept in at least one KS suspected or confirmed lesion by planar and/or SPECT/CT imaging
- Per lesion/region concordance of Tc 99m localization with anatomical areas of active KS defined by confirmed diagnosis or clinical symptomology

- Localization intensity for each biopsied and clinically defined lesion localized on imaging following IV injection as determined by quantitative SPECT gamma counts
- Per biopsied lesion proportion of CD206-expressing cells and proportion of HHV8-expressing cells as determined by histology and relative IHC fluorescence
- Per lesion/region concordance of IV vs SC Tc 99m localization with anatomical areas of active KS defined by confirmed diagnosis or clinical symptomology.
- Per subject localization rate of Tc 99m tilmanocept in areas other than KS by planar and/or SPECT/CT imaging
- Per area localization rate of Tc 99m tilmanocept in the most frequently identified areas other than KS by planar and/or SPECT/CT imaging

An exploratory objective of the study is to use quantitative Polymerase Chain Reaction (qPCR) methods to measure the amount of Human Herpes Virus 8 (HHV8) present in the biopsy tissue.

The relevant variables are the following:

- Nuclear medicine specialist determination of presence/absence of illumination (i.e., localization positive or negative per anatomic site) relative to background from planar and/or SPECT/CT imaging results for each subject;
- Clinically identified presence or absence of KS based on any previous diagnostic evaluation;
- Proportion of CD206-expressing cells (IHC fluorescence);
- Quantitative SPECT gamma counts for each biopsied lesion localized on imaging following IV injection; and,
- HHV8 concentrations as determined by qPCR for each biopsied lesion.

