4.2 Analysis of Efficacy Variables

Localization in KS Sites

The number and percentage of subjects with at least one biopsy-confirmed or clinically suspected KS lesion that has localized with Tc 99m tilmanocept by planar and/or SPECT/CT imaging will be computed. A 95% exact confidence interval on the per-subject localization rate will be computed. This analysis will be performed by dose group and route of administration.

Per-lesion/region localization of Tc 99m tilmanocept by planar and/or SPECT/CT imaging will be computed across all biopsy-confirmed or clinically suspected KS lesions of all subjects. A 95% exact confidence interval on the per-lesion/region localization will be calculated. This analysis will be performed by dose group and route of administration.

An analysis table will also be provided to display the counts of KS lesions localized by imaging that were not previously identified clinically.

Concordance between IV and SC tilmanocept in biopsy-confirmed or clinically-suspected KS lesion sites will be assessed with a cross-tabulation of the IV and SC findings, including the joint probability distribution. The sampling unit for this analysis will be the site. An exact conditional version of McNemar's test will be performed to test the hypotheses

$$H_0: \pi_{IV} = \pi_{SC}$$
$$H_A: \pi_{IV} \neq \pi_{SC},$$

where π_{IV} and π_{SC} represent the probabilities of localization with IV (only) tilmanocept and SC (only) tilmanocept, respectively. In addition, the number and proportion of subjects with concordance and reverse concordance of observed sites of discrete localization of Tc 99m tilmanocept following IV and SC localization will be summarized.

Localization Intensity by Planar and/or SPECT/CT Imaging

Tc 99m tilmanocept average pixel intensity and percent above background will be summarized with descriptive statistics (mean, standard deviation, minimum, median, maximum, and range) for each biopsied lesion localized on imaging following IV injection of Tc 99m tilmanocept by dose group. Summary statistics will be presented separately by imaging type (planar, SPECT/CT).

Proportion of CD206-expressing Cells

Per biopsied-lesion proportion of CD206-expressing cells as determined by histology and IHC fluorescence will be summarized by descriptive statistics (mean, standard deviation, minimum, median, maximum, and range) by dose group.

Localization in Non-KS Sites

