	Female	xxx (xxx%)	xxx (xxx%)	xxx (xxx%)	xxx (xxx%)
Race	American Indian or Alaska Native	xxx (xxx%)	xxx (xxx%)	xxx (xxx%)	xxx (xxx%)
	Asian	xxx (xxx%)	xxx (xxx%)	xxx (xxx%)	xxx (xxx%)
Race	Black or African American	xxx (xxx%)	xxx (xxx%)	xxx (xxx%)	xxx (xxx%)
	Native Hawaiian or Other Pacific Islander	xxx (xxx%)	xxx (xxx%)	xxx (xxx%)	xxx (xxx%)
Race	White	xxx (xxx%)	xxx (xxx%)	xxx (xxx%)	xxx (xxx%)
	Other	xxx (xxx%)	xxx (xxx%)	xxx (xxx%)	xxx (xxx%)
Ethnicity	Hispanic or Latino	xxx (xxx%)	xxx (xxx%)	xxx (xxx%)	xxx (xxx%)
	Not Hispanic or Latino	xxx (xxx%)	xxx (xxx%)	xxx (xxx%)	xxx (xxx%)

Cohort 1 = 100µg/5mCi IV; Cohort 2 = 100µg/10mCi IV; Cohort 3 = 200µg/5mCi IV and SC.
 STAKING Clinical Services (DD-MMM-YYYY)
 Source Program: xxxxxxxx.sas

Page x of y

Table 4. Summary of Study Drug Administration by Cohort
 Navidea Biopharmaceuticals - Study No. NAV3-24
 Safety Population (N=xxx)

	Group	Mean	Std Dev	n	Min	Max	Median
Tc 99m Dose (mCi)	Cohort 1 IV	xxxx	xxxx	xx	xxxx	xxxx	xxxx
	Cohort 2 IV	xxxx	xxxx	xx	xxxx	xxxx	xxxx
	Cohort 3 IV	xxxx	xxxx	xx	xxxx	xxxx	xxxx
	Cohort 3 SC	xxxx	xxxx	xx	xxxx	xxxx	xxxx
Mass Dose (µg)	Cohort 1 IV	xxxx	xxxx	xx	xxxx	xxxx	xxxx
	Cohort 2 IV	xxxx	xxxx	xx	xxxx	xxxx	xxxx
	Cohort 3 IV	xxxx	xxxx	xx	xxxx	xxxx	xxxx
	Cohort 3 SC	xxxx	xxxx	xx	xxxx	xxxx	xxxx

Cohort 1 = 100µg/5mCi IV; Cohort 2 = 100µg/10mCi IV; Cohort 3 = 200µg/5mCi IV and SC.

STATKING Clinical Services (DD-MMM-YYYY)

Source Program: xxxxxxxx.sas

Table 5. Subject-Level Localization of KS Lesions-Nuclear Medicine Findings
 Navidea Biopharmaceuticals - Study No. NAV3-24
 ITD Population (N=xxx)

Group	Number of Subjects	Number (Proportion) Localized	95% Exact One-Sided Binomial CI for Proportion
Cohort 1 IV	xx	xxx (xxx)	(xxx, xxx)
Cohort 2 IV	xx	xxx (xxx)	(xxx, xxx)
Cohort 3 IV	xx	xxx (xxx)	(xxx, xxx)
Cohort 3 SC	xx	xxx (xxx)	(xxx, xxx)
All Cohorts Combined	xx	xxx (xxx)	(xxx, xxx)

Cohort 1 = 100 μ g/5mCi IV; Cohort 2 = 100 μ g/10mCi IV; Cohort 3 = 200 μ g/5mCi IV and SC.
 STATKING Clinical Services (DD-MMM-YYYY)
 Source Program: xxxxxxxx.sas

Table 6. Lesion-Level Localization of KS Lesions-Nuclear Medicine Findings
 Navidea Biopharmaceuticals - Study No. NAV3-24
 ITD Population (N=xxx)

Group	Number of Clinically Identified Lesions ^a	Number (Proportion) Localized by Imaging	95% Exact One-Sided Binomial CI for Proportion
Cohort 1 IV	xx	xxx (xxx)	(xxx, xxx)
Cohort 2 IV	xx	xxx (xxx)	(xxx, xxx)
Cohort 3 IV	xx	xxx (xxx)	(xxx, xxx)
Cohort 3 SC	xx	xxx (xxx)	(xxx, xxx)

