All Cohorts Combined	xx	xxx (xxx)	(xxx, xxx)

^a Number of cutaneous and non-cutaneous lesions identified in screening.

Cohort 1 = 100 μ g/5mCi IV; Cohort 2 = 100 μ g/10mCi IV; Cohort 3 = 200 μ g/5mCi IV and SC.

STATKING Clinical Services (DD-MMM-YYYY)

Source Program: xxxxxxx.sas

Page x of y

Table 7. Additional KS Lesions Identified from Imaging That Were Not Seen Clinically - Nuclear
Medicine Findings
Navidea Biopharmaceuticals - Study No. NAV3-24
ITD Population (N=xxx)

Group	Number of Identified Lesions	Number (Proportion) of Subjects with at Least 1 Identified Lesion
Cohort 1 IV	xx	xxx (xxx)
Cohort 2 IV	xx	xxx (xxx)
Cohort 3 IV	xx	xxx (xxx)
Cohort 3 SC	xx	xxx (xxx)
All Cohorts Combined	xx	xxx (xxx)

Cohort 1 = 100 μ g/5mCi IV; Cohort 2 = 100 μ g/10mCi IV; Cohort 3 = 200 μ g/5mCi IV and SC.
STATKING Clinical Services (DD-MMM-YYYY)
Source Program: xxxxxxxx.sas

Table 8. Lesion-level Non-Localization of KS Lesions - Nuclear Medicine Findings
 Navidea Biopharmaceuticals - Study No. NAV3-24
 ITD Population (N=xxx)

Group	Number of Clinically Identified Lesions ^a	Number (Proportion) Not Localized by Imaging	95% Exact One-Sided Binomial CI for Proportion
Cohort 1 IV	xx	xxx (xxx)	(xxx, xxx)
Cohort 2 IV	xx	xxx (xxx)	(xxx, xxx)
Cohort 3 IV	xx	xxx (xxx)	(xxx, xxx)
Cohort 3 SC	xx	xxx (xxx)	(xxx, xxx)
All Cohorts Combined	xx	xxx (xxx)	(xxx, xxx)

^a Number of cutaneous and non-cutaneous lesions identified in screening.
 Cohort 1 = 100 μ g/5mCi IV; Cohort 2 = 100 μ g/10mCi IV; Cohort 3 = 200 μ g/5mCi IV and SC.
 STATKING Clinical Services (DD-MMM-YYYY)
 Source Program: xxxxxxxx.sas

Page x of y

Table 9. Number and Percentage of Concordant and Reverse Concordant Lesions
Navidea Biopharmaceuticals - Study No. NAV3-24
ITD Population (N=xxx)

IV Result	SC Result		Total	Concordance	Reverse Concordance	p-Value (McNemar's Test)
	Localized	Not Localized				
Localized	xx (xxx%)	xx (xxx%)	xx (xxx%)	xxx (xxx%)	xxx (xxx%)	xxx
Not Localized	xx (xxx%)	xx (xxx%)	xx (xxx%)			
Total	xx (xxx%)	xx (xxx%)				

STATKING Clinical Services (DD-MMM-YYYY)
Source Program: xxxxxxxx.sas

Page x of y

Table 10. Summary of Imaging-Localized Biopsied Lesion Localization Intensity by Cohort -
 Imaging = Planar
 Navidea Biopharmaceuticals - Study No. NAV3-24
 ITD Population (N=xxxx)

Group	Variable ^a	Mean	Std Dev	n	Min	Max	Median
Cohort 2 IV	Avg Pixel Intensity Percent Above Background	xx xx	xx xx	xx xx	xx xx	xx xx	xx xx

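### The clinical concordance endpoint is analysed only as a detection rate in clinically identified KS lesions; Table 8 is its complement, and no planned output gives agreement in KS-negative regions

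*SAP*

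**What the plan says.** SAP 1.0 gives the first secondary objective as "Concordance between clinical assessment/diagnosis and the localization of Tc 99m tilmanocept by planar and/or SPECT" and CT imaging, in cutaneous and non-cutaneous KS sites. SAP 4.1 turns this into the endpoint "Per lesion/region concordance of Tc 99m localization with anatomical areas of active KS defined by confirmed diagnosis or clinical symptomology". Among the variables, SAP 4.1 lists the reader's positive or negative call at each anatomic site, and clinical KS status as present or absent.

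SAP 4.2 then says that localization "will be computed across all biopsy-confirmed or clinically suspected KS lesions of all subjects". SAP 1.1.1 builds in the same restriction: "A localized KS lesion is a lesion that is both clinically identified or suspected KS", and which is also illuminated. Protocol 9.3 and 9.5.3 have the same structure.

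In SAP Appendix B, Table 6 reports "Number (Proportion) Localized by Imaging" out of the clinically identified lesions. Table 8, "Lesion-level Non-Localization of KS Lesions", reports the number not localized out of the same lesions, under the same footnote. Findings away from clinically identified KS go to Tables 7, 14 and 15. The only cross-tabulation is Table 9, which compares IV with SC.

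The lesion form in Protocol Appendix 5 already asks the site to "Indicate if KS-suspicious lesions are absent or present in each of these sites", with 15 skin regions (codes 12 to 26). It has a similar grid for nine oral sites.

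**The concern.** Agreement between two yes/no assessments has two sides: how often imaging is positive where the clinician finds KS, and how often it is negative where the clinician does not. The SAP collects both variables but analyses only the first side. The result labelled concordance is therefore a detection rate. It has the same value for a tracer that localizes only in KS and for one that also localizes focally elsewhere.

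This matters because it is the only planned comparison of imaging with clinical diagnosis. A high Table 6 figure could be quoted as agreement with the clinical map when half of that comparison was never made. Table 8 looks like the missing half but is Table 6 turned round.

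**Working it through.** The documents state no target or expected value for clinical concordance, so there is no planned figure to reproduce.

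**1. Table 8 against Table 6.** Let n be the clinically identified lesions and x the number localized. Table 6 is x/n and Table 8 is (n − x)/n = 1 − x/n. This held for every x and every n from 1 to 300, and the exact bounds are complements too. For example, with 15 of 20 localized:

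- Table 6 is 75%, with one-sided 95% bounds of 54.4% (lower) and 89.6% (upper).
- Table 8 is 25%, with bounds of 10.4% and 45.6%, which are 1 − 0.896 and 1 − 0.544.

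The shells call for one-sided intervals without giving a direction. If both tables print the same direction, Table 8 shows the opposite bound. It can add nothing else.

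**2. Which cells the plan uses.** Cross clinical status with imaging by region:

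| | Localized | Not localized |
|---|---|---|
| KS present | a | b |
| KS absent | c | d |

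Tables 6 and 8 use only a and b. The other outputs compare as follows:

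- Table 7 counts imaging-only lesions, with no denominator of KS-negative regions.
- Table 14 counts subjects with at least one localized non-KS site.
- Table 15 gives a rate for each named site, divided by the number of subjects.
- Data Listing 18 covers clinically identified lesions and additional imaging lesions only.

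Cell d appears in no table or listing, so d/(c + d), called negative agreement here, cannot be rebuilt from the planned outputs. Nor does any rule say whether a focus at a clinically negative location goes to Table 7, as an additional KS lesion, or to Tables 14 and 15, as an area other than KS.

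**3. Illustration.** Inputs from the documents are up to 14 subjects (SAP 1.3), all of whom have an IV scan, and 15 skin regions (Protocol Appendix 5), giving 14 × 15 = 210 regions. The number of KS-positive regions per subject, k, is not in the documents, so it is assumed over a range. Suppose there is focal uptake in every region, and this counts as localization of the lesions there. Then a = 14k, b = 0, c = 14(15 − k) and d = 0. Overall agreement is (a + d)/210 = k/15.

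| k | a | c | Table 6 | Table 8 | Negative agreement | Overall agreement |
|---|---|---|---|---|---|---|
| 2 | 28 | 182 | 100% | 0% | 0% | 13.3% |
| 3 | 42 | 168 | 100% | 0% | 0% | 20.0% |
| 5 | 70 | 140 | 100% | 0% | 0% | 33.3% |
| 8 | 112 | 98 | 100% | 0% | 0% | 53.3% |
| 12 | 168 | 42 | 100% | 0% | 0% | 80.0% |

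Cohen's kappa is 0 in every row. A perfectly specific tracer gives the same Tables 6 and 8, with negative agreement 100% and kappa 1.

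**4. Table 15's denominator.** Suppose 10 of 14 subjects have KS on the right leg and all four KS-free right legs localize (assumed values). The ten subjects with KS there cannot contribute a non-KS positive at that site. Table 15 would show 4/14 = 29%, while the rate among subjects who are KS-negative there is 4/4 = 100%.

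**The case against.** A reader might infer that off-target uptake goes unreported. The documents do not support that. Two of the secondary endpoints address non-KS localization, and Table 7 adds imaging-only lesions. In the illustration, Table 14 would read 14/14 and Table 15 would name the sites. What is missing is agreement in KS-negative regions. Table 14 also may not discriminate well, because uptake at a single non-KS site is enough to count a subject. Protocol 1.2.1 reports lymph-node localization in the earlier KS pilot study.

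A reader might also infer that any diffuse uptake would score as perfect concordance. SAP 1.1.1 requires illumination relative to background, so uptake that raises the background would tend to lower Table 6. The failure case is focal uptake in KS-negative regions.

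The wording of the objective and endpoint can be read as agreement at KS sites only, with non-KS uptake kept as separate endpoints. That reading is coherent. It sits poorly, though, with SAP 4.1 listing absence of KS and negative localization as variables, and on that reading the result should be called detection.

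The form is an imperfect negative reference, and this objection stands. It counts only hyperpigmented lesions and leaves out subcutaneous swelling alone. Protocol 3.2 also aims to evaluate unknown lesions, so a true new finding would count as disagreement. Planar uptake over the chest or abdomen may be visceral or nodal, SPECT/CT is optional, and SC doses go into the ankle or foot. These points shape the fix but do not remove the need for it.

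Finally, this is a small, descriptive Phase 1 study, and the escalation rules in Protocol 5.3 depend on adverse drug reactions. That limits the consequences.

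**Conclusion.** The point holds. The clinical concordance endpoint is analysed as detection among clinically identified KS lesions, Table 8 duplicates Table 6, and no planned output gives agreement in KS-negative regions. These conclusions follow from the definitions and shells alone.

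The range of 13% to 80% overall agreement rests on the 15-region skin grid, an assumed 2 to 12 KS-positive regions per subject, and focal uptake everywhere. It shows what Table 6 cannot detect and is not a forecast for this trial. The 100% in Table 6 and the 0% negative agreement do not depend on the assumed number of regions.

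This should be corrected before analysis because it concerns the first secondary objective. It does not touch the primary safety endpoint or dose escalation.

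**What to change.** 1. Label Table 6 as detection in clinically identified lesions (positive agreement).
2. Replace Table 8 with a descriptive 2x2 over the 15 skin regions on the lesion form: KS-suspicious lesions absent or present, by localized yes or no. Present it by cohort and route. Report positive, negative and overall agreement, with intervals that allow for several regions per subject.
3. State in advance that SC injection-site regions and sites of expected physiologic uptake are shown separately.
4. Keep oral and non-cutaneous sites out of the grid, or collapse them.
5. Describe regions that are imaging-positive but absent on the form as discordant, meaning possible new lesions cross-referenced to Table 7, and not as proven false positives.
6. In Table 15, use as denominator the subjects who are clinically KS-negative at that site.

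The cost is one replaced shell, one changed denominator and a short set of rules. The clinical side is already on the form, and Protocol 8.3 already has localized areas entered in the eCRF. The added work is that the same reader must record uptake by region code, including negative regions, and planar findings must be mapped to those codes. The main limitation is that absence on the form remains an imperfect negative reference, which the table should say in a footnote.

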9.5.3 Analysis of Efficacy Variables

The number and percentage of subjects with at least one biopsy-confirmed or clinically suspected KS lesion that has localized with Tc 99m tilmanocept by planar and/or SPECT/CT imaging will be

computed. A 95% exact confidence interval on the per subject localization rate will be computed. This analysis will be performed by dose.

Per region lesion localization of Tc 99m tilmanocept by planar and/or SPECT/CT imaging will be computed across all biopsy-confirmed or clinically suspected KS lesions of all subjects. A 95% exact confidence interval on per region lesion localization will be calculated. This analysis will be performed by dose.

Localization intensities of biopsied lesions will be summarized by descriptive statistics (mean, median, standard deviation, minimum, maximum and range) for each dose.

Per biopsied lesion proportion of CD206-expressing cells and quantity of CD206 as determined by histology and IHC fluorescence will be summarized by descriptive statistics (mean, median, standard deviation, minimum, maximum and range) for each dose.

Concordance between between IV and SC tilmanocept in biopsy-confirmed or clinically suspected KS lesion sites will be assessed with a cross-tabulation including the joint probability distribution. The site will be the sampling unit for this analysis. An exact version of McNemar's test will be performed, testing the null hypothesis

$$H_0: \pi_{IV} = \pi_{SC}$$

$$H_A: \pi_{IV} \neq \pi_{SC}$$

where π_{IV} and π_{SC} represent the probabilities of localization with IV (only) tilmanocept and localization with SC tilmanocept only respectively.

In addition, descriptive statistics will be generated relative to the concordance and reverse concordance of observed sites of discrete localization of Tc 99m tilmanocept following IV and SC administration.

The number and percentage of subjects with at least one anatomical site other than KS that has been localized with Tc 99m tilmanocept by SPECT imaging will be computed. A 95% exact confidence interval on the per subject localization rate will be computed. This analysis will be performed by dose and overall.

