2.2.1 Subgroup Definitions

Analyses may be performed by dose group (Cohort 1, 100 μ g/5mCi; Cohort 2, 100 μ g/10mCi; Cohort 3, 200 μ g/5mCi) and by route of administration (Cohort 3 SC and IV).

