Cohort 3 IV	Avg Pixel Intensity Percent Above Background	xx xx	xx xx	xx xx	xx xx	xx xx	xx xx
All Cohorts Combined	Avg Pixel Intensity Percent Above Background	xx xx	xx xx	xx xx	xx xx	xx xx	xx xx

^a All summary statistics are performed on the subject level.

Cohort 1 = 100 μ g/5mCi IV; Cohort 2 = 100 μ g/10mCi IV; Cohort 3 = 200 μ g/5mCi IV and SC.

STATKING Clinical Services (DD-MMM-YYYY)

Source Program: xxxxxxxx.sas

Page x of y

Table 11. Summary of Imaging-Localized Biopsied Lesion Localization Intensity by Cohort -
 Imaging = SPECT/CT
 Navidea Biopharmaceuticals - Study No. NAV3-24
 ITD Population (N=xxxx)

Group	Variable ^a	Mean	Std Dev	n	Min	Max	Median
Cohort 2 IV	Avg Pixel Intensity Percent Above Background	xx xx	xx xx	xx xx	xx xx	xx xx	xx xx
Cohort 3 IV	Avg Pixel Intensity Percent Above Background	xx xx	xx xx	xx xx	xx xx	xx xx	xx xx
All Cohorts Combined	Avg Pixel Intensity Percent Above Background	xx xx	xx xx	xx xx	xx xx	xx xx	xx xx

^a All summary statistics are performed on the subject level.

Cohort 1 = 100 μ g/5mCi IV; Cohort 2 = 100 μ g/10mCi IV; Cohort 3 = 200 μ g/5mCi IV and SC.

STATKING Clinical Services (DD-MMM-YYYY)

Source Program: xxxxxxxx.sas

Table 12. Summary of Per Biopsied Lesion Proportion of CD206-Expressing Cells and Proportion of HHV8-Expressing Cells by IHC
Navidea Biopharmaceuticals - Study No. NAV3-24
ITD Population (N=xxxx)

Group	Variable	Mean	Std Dev	n	Min	Max	Median
Cohort 2	Proportion of CD206-Expressing Cells	xx	xx	xx	xx	xx	xx
	Proportion of HHV8-Expressing Cells	xx	xx	xx	xx	xx	xx
Cohort 3	Proportion of CD206-Expressing Cells	xx	xx	xx	xx	xx	xx
	Proportion of HHV8-Expressing Cells	xx	xx	xx	xx	xx	xx
All Cohorts Combined	Proportion of CD206-Expressing Cells	xx	xx	xx	xx	xx	xx
	Proportion of HHV8-Expressing Cells	xx	xx	xx	xx	xx	xx

Cohort 1 = 100 μ g/5mCi IV; Cohort 2 = 100 μ g/10mCi IV; Cohort 3 = 200 μ g/5mCi IV and SC.

STATKING Clinical Services (DD-MMM-YYYY)

Source Program: xxxxxxxx.sas

Page x of y

Table 13. Summary of Per Biopsied Lesion HHV8 Quantitation by qPCR
Navidea Biopharmaceuticals - Study No. NAV3-24
ITD Population (N=xxx)

Group	Variable (Unit)	Mean	Std Dev	n	Min	Max	Median
Cohort 2	HHV8 (RFU)	xx	xx	xx	xx	xx	xx
Cohort 3	HHV8 (RFU)	xx	xx	xx	xx	xx	xx

STATKING Clinical Services (DD-MMM-YYYY)
Source Program: xxxxxxxx.sas

Page x of y

Table 14. Subject-Level Localization in Areas Other Than KS Sites - Nuclear Medicine Findings
Navidea Biopharmaceuticals - Study No. NAV3-24
ITD Population (N=xxx)

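### The SAP drops the protocol's CD206-quantity measure without explanation, and its shells for Tables 10–12 have no Cohort 1 row although its text calls for summaries by dose group

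*SAP*

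**What the plan says.** **CD206 quantity.** The Protocol Synopsis and Protocol 9.3 list one secondary endpoint with two parts: the proportion of CD206-expressing cells and total CD206. Protocol 8.4 gives both as the purpose of the biopsy. Protocol 9.5.3 plans the analysis: "Per biopsied lesion proportion of CD206-expressing cells and quantity of CD206 as determined by histology and IHC fluorescence will be summarized by descriptive statistics", for each dose. SAP 1.0 and the opening of SAP 4.1 keep CD206 quantity in the secondary objective on the optimal IV dose. SAP 4.2, however, plans only this: "Per biopsied-lesion proportion of CD206-expressing cells as determined by histology and IHC fluorescence will be summarized by descriptive statistics", by dose group. Table 12 is titled "Summary of Per Biopsied Lesion Proportion of CD206-Expressing Cells and Proportion of HHV8-Expressing Cells by IHC".

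**Cohort 1.** Protocol 9.5.3 states: "Localization intensities of biopsied lesions will be summarized by descriptive statistics (mean, median, standard deviation, minimum, maximum and range) for each dose". SAP 2.2.1 names the three cohorts as the dose groups ("Analyses may be performed by dose group (Cohort 1", followed by Cohorts 2 and 3). SAP 4.2 summarizes intensity "for each biopsied lesion localized on imaging following IV injection of Tc 99m tilmanocept by dose group". The shells for Tables 10 and 11 ("Summary of Imaging-Localized Biopsied Lesion Localization Intensity by Cohort") and for Table 12 have rows for Cohort 2, Cohort 3 and All Cohorts Combined. The exploratory shell, "Table 13. Summary of Per Biopsied Lesion HHV8 Quantitation by qPCR", has rows for Cohorts 2 and 3 only. Protocol 8.4 has every subject biopsied on the day of IV administration.

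**The concern.** The protocol promises two CD206 measures and the SAP delivers one. The missing one is named in the SAP's own objective, so an analyst following the SAP would finish with part of a protocol secondary endpoint in no table and no listing. The body of the SAP has no section on changes from the protocol that would account for this.

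The row omission is a conflict between text and shells. The text includes Cohort 1 by definition, and the shells leave it out. Imaging intensity is where a dose-specific row is most informative, because Cohort 1 is the dose that differs from each of the other two in one factor only.

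**Working it through.** **1. Where each CD206 measure appears**

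| Place | Proportion of CD206-expressing cells | Total or quantity of CD206 |
|---|---|---|
| Protocol Synopsis, secondary endpoints | yes | yes |
| Protocol 8.4, purpose of biopsy | yes | yes |
| Protocol 9.3, endpoint list | yes | yes |
| Protocol 9.5.3, analysis | yes | yes |
| SAP 1.0 and opening of 4.1, objective | not named | yes |
| SAP 4.1, endpoint list | yes | no |
| SAP 4.1, variable list | yes | no |
| SAP 4.2, analysis | yes | no |
| SAP Table 12 | yes | no |
| SAP Data Listing 19 | yes | no |

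In the SAP 4.1 endpoint sentence, the proportion of HHV8-expressing cells stands where the protocol has total CD206.

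**2. Cohort rows in the efficacy shells**

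| Shell | Cohort 1 | Cohort 2 | Cohort 3 | Combined |
|---|---|---|---|---|
| Tables 5–8, 14, 15 | yes | yes | yes (IV and SC) | yes |
| Tables 10, 11 | no | yes | yes (IV) | yes |
| Table 12 | no | yes | yes | yes |
| Table 13 | no | yes | yes | no |

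SAP 4.2 asks for Tables 10–12 by dose group and excludes no cohort. It has no text for HHV8 by qPCR, so Table 13 has no such sentence to conflict with.

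**3. Number of subjects affected**

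The planned sizes are 4, 4 and up to 6 (Protocol 5.2, SAP 1.3). Their sum, 4 + 4 + 6 = 14, reproduces the stated maximum.

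- Table 12: the cohort rows cover at most 4 + 6 = 10 of 14 subjects (71.4%). The 4 Cohort 1 subjects, 4/14 = 28.6%, have no dose-specific row. If Cohort 3 enrolled only 4, the share would be 4/12 = 33.3%.
- Table 13: the same counts apply, given a biopsy in every subject.
- Tables 10–11: these cover only biopsied lesions that localize on imaging, and SPECT/CT is optional (SAP 6.3). The Cohort 1 count could be 0 to 4, that is 0% to 28.6% of 14.

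**4. What Cohort 1 contributes for intensity**

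| Pair | Mass dose | Activity |
|---|---|---|
| Cohort 1 (100 µg/5 mCi) and Cohort 2 (100 µg/10 mCi) | same | differs |
| Cohort 1 and Cohort 3 (200 µg/5 mCi) | differs | same |
| Cohort 2 and Cohort 3 | differs | differs |

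Both pairs that differ in one factor involve Cohort 1. With rows for Cohorts 2 and 3 alone, a reader of Tables 10–11 sees only the pair in which mass and activity change together.

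**The case against.** Several points on the other side stand.

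- A reader might infer that the SAP leaves it open whether text or shells govern. Appendix A says otherwise on format: the mock tables are the format of the deliverables and the sponsor agrees to them as shown. That does not show that leaving out Cohort 1 was intended, but it makes programming from the shells the likely course.
- A reader might extend the single-factor argument to Tables 12 and 13. Those report properties of tissue biopsied on the day of imaging, and the documents give no reason why these should vary with tracer mass or activity. The argument fits intensity only. Even there, SAP 4.2 and Protocol 9.5.3 plan no comparison between doses, and SAP 2.1 makes all results descriptive.
- A reader might infer that the combined row leaves out Cohort 1. The plain words mean all cohorts, and in Tables 5–8, 14 and 15 the same label sits beneath a Cohort 1 row. A confirming sentence is enough.
- Cohort 1's individual values would remain in Data Listings 17 and 19. With at most 4 planned subjects, a reader could largely rebuild the missing row.
- The proportion of CD206-expressing cells is itself a quantitative measure and partly serves the objective. One of two CD206 measures is lost, not CD206 as a whole.

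The listings do not rescue total CD206, because Data Listing 19 has no column for it.

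It might also be supposed that nothing localized in Cohort 1. The documents do not say so. That could explain Tables 10–11 but not Table 12, because Protocol 7.2.3 and 8.4 provide for biopsy of another lesion when none localizes.

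**Conclusion.** Both defects hold and should be fixed. The loss of CD206 quantity is the more serious: one of the two measures in a protocol secondary endpoint would be reported nowhere, with no reason given. The Cohort 1 omission removes the promised summary for one of three IV doses from Tables 10–12. It affects up to 4 of 14 subjects in Table 12 and 0 to 4 in Tables 10–11. Table 13 has the same gap, but as an exploratory table with no analysis text in SAP 4.2 it is a matter of consistency.

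The documents do not support reading this as a failure of the dose-escalation assessment. The outputs are descriptive, secondary or exploratory, and the primary endpoint, the proportion of subjects with an adverse drug reaction, is unaffected.

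The counts assume enrolment of 4, 4 and 6 with a biopsy in every subject. The conclusion on missing explanations rests on the body of the SAP; its opening pages were not available. Extraction loss is an unlikely cause of the missing rows, because Tables 11, 12 and 13 are intact and all lack Cohort 1.

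**What to change.** 1. Restore total CD206 to the SAP 4.1 endpoint and variable lists, SAP 4.2, Table 12 and Data Listing 19, or record in the SAP why it was dropped.
2. Add a Cohort 1 row to Tables 10, 11 and 12, and to Table 13 for consistency, or state why those data do not exist. If no Cohort 1 lesion localized, a row with n = 0 in Tables 10–11 would say so.
3. Confirm in a footnote that All Cohorts Combined includes Cohort 1.

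The cost is shell and text edits with minor programming. Appendix A applies charges to changes in table format made after the SAP is approved. The documents do not show whether Cohort 1 biopsy data exist, or whether the image analysis program reports total CD206 separately from the proportion. If either is unavailable, one explanatory sentence in the SAP settles that part.
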